### Per-Protocol Population (PP)

This population includes all participants who are paired with a dog.

### Safety

This population includes all subjects who have signed informed consent. Adverse events are recorded for the duration of the participant's study participation and may include serious adverse events for up to one month after participation ends.

## 5.3 Missing Data and Imputations

The primary analyses will analyze the data as observed.. In the hopefully unlikely event that a dog needs to be replaced after pairing (e.g., dog dies, gets hurt, becomes aggressive), then the participant's data will be included in the analysis up to this point. The participant will still be offered another dog and will remain enrolled in the study for the remainder of the 18 months. Data will be collected after the dog has been replaced, however it will not be used in the primary analysis.

However, some missing data will arise. When missing data are encountered in the analyses and considered substantial, a detailed sensitivity analysis will be conducted on the effects of various assumptions about the missing data. Within the taxonomy of Little and Rubin, mechanisms will be a mixture of missing completely at random (MCAR), missing at random (MAR), or missing not at random (MNAR). MAR assumes that missing status is due purely to observed variables while MNAR allows missing status to also depend on the value of the missing datum. An example of MCAR is when a participant moves away. The sensitivity of results to assumptions about the missing-value mechanism

(MAR and MNAR) will be examined by analyzing the data with methods appropriate to each. Multiple imputation will be performed under the assumption that missing data are MAR (Little and Rubin, 2002). Assuming MNAR, we will fit the data to pattern-mixture models, assessing sensitivity to various identifying restrictions, as needed (Thijs et al., 2002).

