If reasonable interventions by VA Dog Trainers in consultation with vendor staff members cannot correct the situation, the dog will be returned to the vendor and a replacement may be sought. The decision to return a dog to the vendor will be made by the study national dog trainer, COR and/or CVMO, in consultation with the study chair, and other study leadership and team members. These situations will be dealt with on a case-by-case basis. Data will be collected for all replacement dog post pairing visits, but in most cases will not be used for the main analysis because data from these participants may skew findings.

Replacement dog procedures include a number of components to help prepare for the new pairing and support the participant and dog bonding process. These procedures include:

- The participant will be required to attend another training session at the vendor location (for a Service Dog) or schedule another placement session by a VA Dog Trainer (for an Emotional Support Dog).
- Post-pairing Outcome visits (months 3, 6, 9, 12, 15, 18) will continue on the pre-existing visit schedule. This overall study timeline will not reset.
- The participant will complete a new schedule of post-pairing monitoring visits (weeks 1 & 2, months 1 & 2). These visits will overlap, not extend, the overall study timeline.
- Guidelines for overlapping visits: If post-pairing monitoring visits overlap existing outcome visits (Months 3-18), these visits can be merged based on the guidelines below. Note that one exception to this merged schedule is related to the 15 Month visit in which the CAPS should be administered in the clinic.

Monitoring Visit	Outcome Visit	Merged visit type
Home	Home	Home. Payment=\$10.
Home	Clinic	Home. Payment=\$10.
Phone	Home	Home. Payment=\$10.
Phone	Clinic	Clinic. Payment=\$25.

- Veterinary Checklist visits will reset starting with week 1.
- Staff will work with the local dog trainer and National Dog Trainer (as needed) to coordinate the pairing or placement process. For additional information see pairing and placement procedures within the Home Clearing Visit section.
- **Permanent removal of a study dog (Cessation of Intervention)**

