In order to detect a 10-point difference in treatment group mean scores for the WHO-DAS 2.0 over the 18 months of follow-up, at a statistical significance level of 0.05 (two-tailed test) and a power of 0.85, 32 participants per group will be needed (see Table 6). In order to detect a 15% difference in mean scores for MCS over the 18-months of follow-up, at a statistical significance level of 0.05 (two tailed test) and a power of 0.85, 82 participants per group will be needed (see Table 6). In order to detect a 15% difference in mean scores for the PCS over the 18-months of follow-up, at a statistical significance level of 0.05 (two tailed test) and a power of 0.85, 60 participants per group will be needed (see Table 6). The sample size estimates were obtained using the PC-software SAS 9.2.

Assuming the largest of the three sample sizes, 82 participants per group, and a maximum of 25% participant loss or dropout rate a sample size of 110 participants per treatment will be required for this study. To obtain the necessary sample size of 220 participants, at least three VA medical centers will be recruited. Once a participant has been determined to be eligible for the study at the participating VA medical center, randomization to one of the two groups will be accomplished by a telephone call to the Perry Point Coordinating Center. All sites will be encouraged to recruit and enroll participants faster than the stated requirements.

- **Statistical Methods**

The intent-to-treat population (ITT) is defined as the population of participants who will be randomized in either the Service Dog (SERV) or Emotional Support Dog (EMOT) treatment groups. The participants will be categorized based on their initial randomized group assignment and will be included in analyses irrespective of their status – completer or drop out of the study before completion. A per protocol population (PP) is defined as the population of participants who are paired with a dog. Analyses of all outcome measures – primary and secondary – will use both the ITT and PP population.

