### Intent-to-Treat (ITT)

This population includes all subjects who are randomized to the study.

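### SAP 5.3 drops outcomes collected after a study dog is replaced from the primary analysis. This departs from the protocol's as-randomized rule and leaves the effect being estimated unstated.

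*SAP*

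**What the plan says.** SAP 5.3 opens by saying the primary analyses use the data as observed. For a dog replaced after pairing, it then says the participant's "data will be included in the analysis up to this point", that the participant is offered another dog and stays enrolled for the rest of the 18 months, and: "Data will be collected after the dog has been replaced, however it will not be used in the primary analysis". No exception is given.

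Protocol section XI (Dog Removals, temporary removals resulting in a replacement dog) says data are collected at all visits after re-pairing, "but in most cases will not be used for the main analysis because data from these participants may skew findings". It also says: "Post-pairing Outcome visits (months 3, 6, 9, 12, 15, 18) will continue on the pre-existing visit schedule". So the outcomes will exist.

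Protocol section XVIII (Statistical Methods) assigns participants to their initial randomized group and says they "will be included in analyses irrespective of their status – completer or drop out of the study before completion". It runs every outcome in both the ITT and the per-protocol population and names neither as primary. SAP 5.2 defines ITT as follows: "This population includes all subjects who are randomized to the study". For per-protocol it says: "This population includes all participants who are paired with a dog".

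SAP 5.3 also plans multiple imputation under missing at random (MAR) and pattern-mixture models under missing not at random (MNAR), if missing data are judged substantial.

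**The concern.** Replacement happens after randomization. SAP 5.3 gives a dog's death, injury or aggression as examples, and Protocol section XI adds failed bonding. Some of these may be related to how the participant is doing, and they may not be equally frequent with Service Dogs and Emotional Support Dogs. Cutting follow-up at such an event means the SERV versus EMOT contrast is no longer the effect of being assigned a dog type, which is what an as-randomized analysis estimates.

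The cut belongs to neither defined population. A re-paired participant is still randomized and still paired with a dog. After a dog's death, Protocol section XIII says the replacement is of the same type, so that participant remains on the assigned intervention. Follow-up without a dog after permanent removal is labelled intent to treat in Protocol section XI, and SAP 5.3 does not expressly exclude it. Read literally, visits without any dog may count while visits with a replacement dog do not.

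Two details are also undefined. The plan does not say whether the cut falls when the first dog leaves or when the new one arrives, although visits continue during temporary removals. It does not say whether someone who refuses a replacement meets the SAP trigger.

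**Working it through.** **1. The rules side by side**

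| Source | Post-replacement outcomes |
|---|---|
| SAP 5.3, opening sentence | Data analysed as observed |
| SAP 5.3, replacement rule | Collected; never in the primary analysis |
| Protocol XI | Collected; left out in most cases, no criteria |
| Protocol XVIII | Analysed by randomized group regardless of completion |
| SAP 5.2 (ITT, PP) | Define who is analysed; silent on which visits |

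The first four cannot all be followed. SAP 5.2 is not contradicted word for word. The tension becomes practical for early replacements. Protocol XI says bonding failures usually occur within two weeks, and the first post-pairing outcome visit is Month 3. A participant whose dog is replaced before Month 3 could contribute few or none of the six post-pairing outcomes.

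**2. What the cut estimates.** SAP 7.1 uses a mixed model on repeated measures. Treating the cut visits as missing makes the model project each replaced participant from earlier visits and from others in the same arm. Under MAR, that is the outcome had the first dog not been replaced. This is an inference from the method, because no passage states it.

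**3. The plan's sample size reproduces.** Inputs (Protocol Table 6, SAP 3.8): MCS mean 33.2, SD 10.6, 15% difference, two-sided 0.05, power 0.85.
- Difference: 0.15 × 33.2 = 4.98.
- n per group: 2 × (1.960 + 1.036)² × 10.6² / 4.98² = 81.4, so 82.
- Inflation: 82/0.75 = 109.3, so 110. Fallback: 72/0.80 = 90.

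There is no arithmetic error.

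**4. Size of the gap (assumed values only).** The documents give neither a replacement rate nor a post-replacement decrement. If the decrement D is equal in both arms and not visible before replacement, the gap between the cut and as-randomized estimates, averaged over the six visits, is

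(rate in SERV − rate in EMOT) × D × share of visits cut.

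Take D = 5 points.
- All replaced before Month 3, all six visits cut, 15% v 5%: 0.10 × 5 × 1 = 0.50 points; 0.50/4.98 = 10%.
- Timing spread evenly (replaced just before visit 1, 2, … or 6): share cut = (6+5+4+3+2+1)/36 = 0.583; gap 0.10 × 5 × 0.583 = 0.29 (6%).
- Even timing with the full decrement already visible beforehand: the model recovers part, leaving 0.15–0.18 (3–4%). This assumes compound symmetry with correlation 0.4–0.7.
- At 10% v 5%, the three gaps are 0.25, 0.15 and 0.08–0.09.

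The gap is zero with equal rates, timing and decrements. It changes sign if the rates are swapped between arms or if outcomes improve after replacement.

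**5. Power at Month 18, MCS (two-sample t-test).** If replacements fall within the 25% allowance, nothing is lost. If they come on top of it, the lower n adds the two losses and the higher n multiplies them.

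| Assumed replacement | 110 per arm, 25% loss: n, power | 90 per arm, 20% loss: n, power |
|---|---|---|
| 0% | 82.5, 0.851 | 72, 0.800 |
| 5% | 77–78.4, 0.826–0.832 | 67.5–68.4, 0.773–0.779 |
| 10% | 71.5–74.25, 0.797–0.812 | 63–64.8, 0.744–0.756 |

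These values ignore what the mixed model recovers from earlier visits, so they are slightly pessimistic.

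**The case against.** The exclusion is prespecified and reasoned: the sponsor fears these data may distort the findings. It removes visits rather than participants, and pre-replacement data stay in the randomized arm. The protocol's as-randomized sentence explains status as completing or dropping out and does not mention replacement. SAP 5.3 plans MAR and MNAR analyses. All of that is true. What remains is that the plan holds incompatible rules and states no target. The planned sensitivity analyses apply only if missingness is substantial, and none brings back data that were actually collected.

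Four stronger readings are tempting and are not supported.
- That the SAP's ITT definition is flatly contradicted. It says who is analysed, not which visits.
- That staff who know the arm will choose whose data count. The sentence "These situations will be dealt with on a case-by-case basis" follows the one on deciding to return a dog to the vendor and does not concern data selection. The protocol has final analyses done by coordinating-centre statisticians under the SAP, whose rule has no exceptions. SAP 5.5 keeps comparative results from the Study Chairmen and Executive Committee.
- That early bonding failure always costs all six outcomes. The two-week figure is for failure, not replacement. Trainer intervention and a new training or placement session come in between, and the cut date is undefined.
- That the result is biased in a known direction or by a large amount. Nothing in the documents fixes either.

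**Conclusion.** The concern holds as an unresolved conflict and an unstated estimand, and it should be fixed before the final analysis. It does not rest on a demonstrated bias. Under the assumed rates (10–15% v 5%) and a 5-point decrement, the primary MCS contrast could shift by about 0.1–0.5 points, at most 10% of the design difference. The top of that range takes a threefold difference in replacement rates and a decrement as large as the whole design effect. If replacements exceed the loss allowance, power falls from 0.85 to about 0.83 at 5% and 0.80–0.81 at 10%. At the fallback of 180 it falls from 0.80 to about 0.77–0.78 and 0.74–0.76. Confidence is high on the textual conflict. Size and direction cannot be judged from the documents.

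**What to change.** In SAP 5.3, replace the cut rule with wording such as:

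> In the ITT analysis, all outcomes observed after a study dog is removed or replaced are included under the randomized arm. A sensitivity analysis excludes outcomes from the date the first dog leaves the participant, if that dog is later replaced. Counts and timing of removals and replacements are reported by arm.

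State whether ITT or per-protocol is the primary population. Delete the qualifier in Protocol XI that limits the exclusion to most cases, and reconcile that passage with Protocol XVIII and SAP 5.3. If the sponsor prefers to keep the cut as primary, SAP 5.3 should instead state the hypothetical effect and its MAR assumption and define the cut date, and Protocol XVIII should be amended to match.

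The cost is one SAP paragraph, a statement of the primary population, and short protocol edits. No new data are needed, because outcome visits already continue on schedule. The downside is that the first-dog-only estimate the sponsor preferred becomes a sensitivity analysis.

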#### **5.4 General Considerations**

This section details general policies to be used for the statistical analyses. Departures from these general policies may be given in the specific detailed sections of this statistical analysis plan. When this situation occurs, the rules set forth in the specific section take precedence over the general policies. The following policies will be applied to all data presentations and analyses.

- All p-values will be rounded to 3 decimal places. All p-values that round to 0.000 will be presented as ‘<0.001’ and p-values that round to 1.000 will be presented as ‘>0.999’. Any p-value  $\leq \alpha$  will be considered statistically significant and will be marked with one asterisk (e.g., 0.026\*).
- Summary statistics will consist of the number and percentage of responses in each category for discrete variables, and the mean, median, standard deviation (SD), minimum, and maximum for continuous variables.
- All mean and median values will be formatted to one more decimal place than the measured value. Standard deviation values will be formatted to two more decimal places than the measured value.
- All percentages will be rounded to one decimal place. The number and percentage of responses will be presented in the form XX (XX.X), where the percentage is in the parentheses. The decimal of the percentage may be dropped due to space constraints when creating a table.
- All listings will be sorted for presentation in order of treatment group, site number, subject number, and date of procedure or event.
- When necessary for analysis purposes, partial dates will be completed (i.e., turned into complete dates) using the most conservative approach.
- All analysis and summary tables will have the population sample size for each group or treatment group in the column heading.
- The baseline for the WHO-DAS 2.0, PCL, PSQI, VR-12, C-SSRS and PHQ-9 is the Home Visit (or Baseline Visit).
- Version 9.3 of SAS® or higher will be the statistical software package used to produce all summaries, listings, statistical analyses, and graphs.
- Updated version of MedDRA will be used for adverse event and pre-treatment coding.
- The current version of the World Health Organization (WHO) drug dictionary will be used for the coding of medications.

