A separate written HIPAA authorization for the use of individually identifiable health information must be signed by the research participant.

Data will be retained after the end of the study as per VA and IRB regulations.

VII. EVALUATION PROCEDURES

Table 5 provides a summary of forms and data collection tools. Each test measure is described in more detail following the table.

Table 5: Summary of Forms and Data Collection Tools

Form	Purpose	When Completed	Who Completes
Mental Health Referral Checklist and Cover Letter	To provide referral for potential participant to participate in research study	Prior to consent	Mental health provider
Veteran Characteristics (form 01)	To collect information about participants	Screening	Member of study team
CAPS (form 03)	PTSD eligibility	Clinic Qualifying visit, Month 15	Trained Mental Health professional on study team
MINI (form 04)	Psychiatric disorders; Determine eligibility	Clinic Qualifying visit,	Qualified mental health professional on study team
Suitability to Have a Dog Checklist (form 05)	Home assessment checklist to assess suitability home environment for dog placement	Home Qualifying visit, Home Clearing Visit, ad hoc visits as needed	VA Dog Trainer (National or local) or another trained individual
Dog Care Test	Test to assess knowledge learned by participant following Dog Care Course	After completing the Dog Care Course, Home Clearing visit	Participant
C-SSRS (form 11)	Suicide assessment	Clinic Qualifying Visit, Baseline 2 visit, and at months 3, 6, 9, 12, 15 and 18	Completed in interview format
WHO-DAS 2.0 (form 07)	Quantification of outcomes	Baseline 1 visit, Baseline 2 visit, and at months 3, 6, 9, 12, 15 and 18	HERC non-VA care and WPAI completed in interview format; remaining measures completed in pen and paper format by participant.
PCL-5 (form 08)			
PSQI (form 09)			
VR-12 (form 10)			
PHQ-9 (form 12)			
DAR (form 13)			
HERC non-VA			

Form	Purpose	When Completed	Who Completes
Inpatient and outpatient Care (form 14)			
WPAI: GHP v2.0 (form 15)			
Post-Pairing Evaluation (form 19)	Assessment of dog-related issues	One week post pairing and as needed	VA Dog Trainer (national or local)
Medication Log (form 17)	Record all Non-VA prescribed medications the participant is taking during the trial	Baseline 1, Baseline 2, Months 3, 6, 9, 12, 15, 18	Study Team

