- Suitability to Have a Dog Checklist: A home assessment checklist to assess suitability of the home environment for dog placement. The checklist documents availability of space for dog to play, availability of space for toileting of dog, the presence of other pets in the home, and cleanliness and safety of the home. The measure was developed specifically for this study because no other such measure exists.

- **Screening Phase**

1. Preliminary Screening:

- Prior to scheduling a potential participant for a clinic qualifying visit the potential participant's chart notes will be examined to determine whether there are indications that the potential participant is ineligible for the study and whether he/she has ongoing mental health treatment at VA.
- A telephone screening will be completed to assess eligibility and thoroughly explain the study procedures.
- A referral letter from mental health provider will be obtained, or confirmation that a signed referral letter will be available by clinic qualifying visit will be obtained.
- In order to help manage expectations, potential participants should be informed that the screening phase is an ongoing process and that final eligibility will not be determined until the successful completion of the dog Placement or Pairing process.

If any CPRS note, the telephone screen, or other information indicates a potential participant is ineligible, the LSI or a designated member of the study team will inform the individual that they cannot participate in the study.

2. Activities prior to Clinic Qualifying Visit.

- If a signed referral checklist has not been received from a mental health provider in advance of the scheduled Clinic Qualifying visit, a member of the study team must confirm by telephone prior to the visit that the potential participant will be bringing it in person to the appointment. If confirmation is not received, the Clinic Qualifying visit must be rescheduled.

- A member of the study team will make a reminder call to the potential participant. If applicable, the potential participant will be reminded to bring the signed referral checklist to the appointment.

3. Clinic Qualifying Visit at VA study site.

- Informed consent and HIPAA authorization will be obtained.
- If not already received, the referral checklist/letter will be collected.
- The Demographic interview and CAPS will be completed
- The C-SSRS will be administered using the ‘during the last month’ time frame.

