- If the participant meets the screening criteria for the CAPS, the MINI will be completed.
- If the individual meets CAPS and MINI inclusion criteria he/she will be provided with the Home Suitability Guide.
- The participant will be informed that secondary contact information for an emergency contact and dog caretaker will be collected no later than the Home Clearing Visit in order to be eligible for the pairing process.
- Veteran will be paid \$25.00 for this first Screening Visit.

4. Home Qualifying Visit and Baseline Assessments

If the individual meets the Clinic Qualifying visit criteria, a home visit will be scheduled within 3 weeks of the Clinic Qualifying visit, unless holiday schedules or an unusual circumstance such as veteran illness prevents the visit within that time frame. In such circumstances, the home visit will be completed as soon as possible. The home visit is conducted to ensure that the potential participant’s home environment is suitable for a dog. The visit will be conducted by one of the study dog trainers and another member of the study team.

- All individuals who reside at the home should be present during the visit if possible. They will be asked whether they are willing to have a dog in their home and be responsible for the dog in the long-term absence of the potential participant (e.g. if individual was admitted to the hospital).
- It will be emphasized to potential participants that they should at minimum maintain a residence in the same locality but ideally should stay in the same home throughout the enrollment period because of the necessity to conduct home visits throughout. If a potential participant changes residence while enrolled in the study, he/she must be informed that the new home must be suitable for a dog and that the new home must be geographically and structurally accessible to the study team.
- The “Suitability to Have a Dog Checklist” will be used to assess the home environment.
- If needed, the participant will be provided with information to share with their homeowners association and/or rental agency regarding the allowance of having a dog in their home. This information includes the rights of Emotional Support Dogs protected under the Department of Justice fair housing and Service Dogs protected under the American with Disabilities Act.
- Participants will be encouraged to ensure that their home owner/rental insurance policy includes a dog.

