- If the home is deemed suitable or only minor modifications are required, baseline assessments will be completed.
- If the home is deemed unsuitable for a dog, the potential participant will be given a detailed list of corrections needed, a second home qualifying visit will be scheduled, and Baseline assessment will NOT be completed. At that visit, if the home is now deemed suitable for a dog, baseline assessments will be completed. If still unsuitable the participant may be ineligible to continue in the study. However, exceptions can be made at the discretion of the dog trainer.

The following baseline assessments will be administered:

1. WHODAS 2.0.

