### 3.6 Forms for Screening, Baseline, Observational and Clearing Visits

The following forms will be used during the screening visit, home visit, observational phase and clearing visit of the study.

*Table 1. Screening and Clearing Data Forms*

Form #	Form Name	Screening	Home/Baseline	Clearing Visit 1	Clearing Visit 2
	PHASE	0	0	1	1
	VISIT #	01	02	01	02
	Location	Clinic	Home	Clinic	Home
86	Informed Consent Confirmation	R			
1	Demographics	R			
2	Veteran Characteristics	R			
3	CAPS	R			
4	MINI	R			
5	Suitability for a Dog		R		R
7	WHO-DAS 2.0		R	R	
8	PCL		R	R	
9	PSQI		R	R	
10	VR-12		R	R	
11	C-SSRS	R		R	
12	PHQ-9		R	R	
13	DAR		R	R	
14	HERC Non-VA Utilization		R	R	
15	WPAI: GHP v2.0		R	R	
16	Inclusion/Exclusion & Randomization				R
17	Medication Log	A	A	A	A
18	Payment Log	A	A	A	A
25	Protocol Deviation	A	A	A	A
26	Adverse Events	A	A	A	A

26a	Adverse Events for Dogs	A	A	A	A
27	Serious Adverse Events	A	A	A	A
27a	Serious Adverse Events for Dogs	A	A	A	A
28	AE/SAE Follow-up	A	A	A	A
28a	SAE Follow-up for Dogs	A	A	A	A

R= REQUIRED

A = AS NEEDED

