#### 6.3.6 C-SSRS

The number and percentages of participants with suicidality will be reported for the baseline visit.

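### SAP 5.4 takes the C-SSRS baseline from the Home/Baseline Visit, where no C-SSRS is scheduled

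*SAP*

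**What the plan says.** SAP 5.4 lists policies for all presentations and analyses, and lets a more specific section override them. One bullet reads: "The baseline for the WHO-DAS 2.0, PCL, PSQI, VR-12, C-SSRS and PHQ-9 is the Home Visit (or Baseline Visit"). SAP 6.3.6 applies it to the C-SSRS: "The number and percentages of participants with suicidality will be reported for the baseline visit".

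The schedules say otherwise. In SAP 3.6, "Table 1. Screening and Clearing Data Forms" requires the C-SSRS at Screening and at Clearing Visit 1, and its Home/Baseline cell is blank. Protocol Table 5 gives the C-SSRS times as "Clinic Qualifying Visit, Baseline 2 visit, and at months 3, 6, 9, 12, 15 and 18", whereas the WHO-DAS 2.0, PCL-5, PSQI, VR-12 and PHQ-9 are due at "Baseline 1 visit, Baseline 2 visit, and at months 3, 6, 9, 12, 15 and 18".

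The protocol's account of the Clinic Qualifying Visit agrees: "The C-SSRS will be administered using the" last-month time frame. Its Home Qualifying Visit section introduces a nine-item list with "The following baseline assessments will be administered", and the C-SSRS is not on that list.

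**The concern.** The SAP's rule for the C-SSRS baseline points to a visit at which the instrument is not given. A programmer who followed 5.4 exactly would find no baseline suicidality value for any participant, and the 6.3.6 summary would be empty.

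A programmer who noticed the gap would have to choose between two pre-pairing values without guidance. One comes before randomization and is also the eligibility measure. The other comes after randomization and at least three months after the Home Visit. An SAP exists so that such a choice is made before the data are seen. At stake are a descriptive table and any baseline value that might be used for Hypothesis 2b on thoughts of suicide.

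**Working it through.** No power or sample size figure is involved. The check sets the baseline rule beside each schedule.

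| Source | WHO-DAS 2.0, PCL-5, PSQI, VR-12, PHQ-9 | C-SSRS |
|---|---|---|
| SAP 5.4 (the rule) | Home/Baseline | Home/Baseline |
| SAP Table 1 | Home/Baseline and Clearing Visit 1 | Screening and Clearing Visit 1; Home/Baseline blank |
| Protocol Table 5, before pairing | Baseline 1 and Baseline 2 | Clinic Qualifying and Baseline 2 |
| Protocol VII, Clinic Qualifying Visit | not listed | given |
| Protocol VII, Home Visit list (9 items) | all five | absent |
| Protocol VIII, Baseline 2 list (11 items) | all five | third item |

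**Counts.** Of the 6 instruments in the 5.4 bullet, 5 are scheduled at Home/Baseline, so 6 − 5 = 1 does not fit: the C-SSRS. It is scheduled 2 times before pairing and 6 times after (months 3, 6, 9, 12, 15 and 18), 2 + 6 = 8 in all. None of the 8 is at the visit that 5.4 names. Two tables and the visit lists agree, so a table damaged in extraction is not the explanation.

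**Does a specific section override 5.4?** None redefines the C-SSRS baseline. SAP 6.3.6 names no different visit. Table 1 shows that the rule cannot be followed, but does not say which value replaces it. SAP 3.7 says that every primary and secondary outcome is collected at baseline, which Table 1 does not bear out for the C-SSRS if baseline means the Home Visit. SAP Appendix 1 Table 6 places the eligibility C-SSRS at the baseline visit, while exclusion criterion 4 in SAP 3.3.2 places it at the Clinic Qualifying Visit.

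**The two candidate values.**
- *Screening / Clinic Qualifying Visit.* The protocol says that "a home visit will be scheduled within 3 weeks of the Clinic Qualifying visit", with exceptions; SAP 3.2 says about one week. Under Protocol VIII, randomization follows the home evaluation and eligibility check, so this C-SSRS precedes it.
- *Clearing Visit 1 / Baseline 2.* Protocol VIII sets it at least three months after the Baseline visit, and SAP 3.5 puts the observation phase after randomization. Participant and site are unblinded only once the Home Clearing Visit (Clearing Visit 2) is completed.

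The two values are therefore at least about three months apart, and lie on opposite sides of randomization.

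**The case against.** The best defence is that the SAP shows what it means. Table 1 puts Screening and Home/Baseline together in phase 0, with the clearing visits in phase 1, and phase 0 holds exactly one C-SSRS. Table 6 uses the baseline-visit label for that same eligibility assessment. On this view an empty table is unlikely in practice. The inference is reasonable and supports Screening as the natural choice, but 5.4 names the Home Visit expressly and nothing in the SAP withdraws that.

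It can also be said that Clearing Visit 1 is a respectable baseline: the protocol calls it Baseline 2, and neither participant nor site knows the arm when it is collected. That is correct, and it is why the SAP has to choose. It does not give the SAP a baseline at the Home Visit.

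A reader might go further and infer that Hypothesis 2b cannot be tested, because SAP 2.1 speaks of examining change for all the hypotheses that follow. That sentence stands under Objective 1, directly before Hypotheses 1a and 1b, and concerns change over the intervention period; 2b has its own heading. SAP 7.2.1 plans a mixed model for thoughts of suicide and logistic regression for suicidality, and states neither a change score nor a baseline covariate. The planned comparison of arms can be run without a baseline value.

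A reader might also subtract 220 paired from about 300 consented (300 − 220 = 80) to bound how many lack a Clearing Visit 1 value. This is not a bound: the consented figure is approximate and includes people lost before randomization, and SAP 3.8 allows an aim of 180, which would give 300 − 180 = 120.

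**Conclusion.** The point holds as an internal contradiction: the stated baseline rule cannot be applied to the C-SSRS. Literally followed, it leaves the 6.3.6 summary without data and any baseline for Hypothesis 2b undefined between two visits.

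Its reach is small. It affects 1 of 6 instruments, a descriptive summary and a secondary outcome. The WHO-DAS 2.0 and VR-12 are scheduled at the Home Visit as 5.4 says, so the primary outcomes stand, as does the planned sample size. It would be wrong to infer that baseline suicidality data are lost: a pre-randomization C-SSRS is already scheduled.

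Calling Screening the only pre-randomization C-SSRS rests on the text of Protocol VIII and SAP 3.4 and 3.5. SAP Table 1 lists the combined eligibility and randomization form (form 16) at Clearing Visit 2, which sits awkwardly with that text. Even if the order of randomization were disputed, the conflict between 5.4 and Table 1 would remain.

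**What to change.** Amend the SAP before it is finalised:

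- **5.4:** remove the C-SSRS from the Home Visit bullet and state that its baseline is the Screening (Clinic Qualifying) Visit, the only C-SSRS before randomization.
- **6.3.6:** report suicidality for that visit. Note that exclusion criterion 4 removes people who endorse question 5 or carry a CPRS flag for suicidal intent, so the count will be low.
- **7.2.1:** keep the Clearing Visit 1 (Baseline 2) value in the by-time-point summary already planned, labelled as the last pre-pairing value.
- **3.7 and Appendix 1 Table 6:** align the C-SSRS visit with Table 1 and exclusion criterion 4.

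The cost is wording only. Both values are already collected, and no visit, sample size or SAP 7.1 analysis changes. One caution for reporting: because the screen lowers the starting count, a later rise within an arm may reflect selection. The screen precedes randomization and applies to both arms, so it does not bias the comparison between them.
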